### 10.1 Adverse Events

An AE will be defined as any unfavorable or unintended change in structure, function, signs, or symptoms temporally associated with the conduct of this study whether or not a causal relationship with the study has been established. The participants will be asked to spontaneously report any AE. Date of onset and resolution (if applicable) of the AE will be documented. The PIs will monitor all AEs to the termination of subject involvement in the study or to a satisfactory resolution if the AE is ongoing.

Events will be considered study-related if classified by the PIs as definitely not, probably not, possibly, probably, or definitely related according to the definitions in Table 7.

Table 7 Defining Relatedness for Adverse Events

Relatedness	Definition
Definitely	The event is definitely not associated with study.

Not	
Probably Not	The temporal association, patient history, or clinical condition is such that the study is not likely to have had an association with the observed event.
Possibly	The event: a) follows a reasonable temporal association with the study procedures, but b) could have been produced by the patient's clinical condition or other therapy.
Probably	The event: a) follows a reasonable temporal association with the study conduct, b) abates upon discontinuation of study procedures, and c) cannot be reasonably explained by the patient's clinical condition or other therapy.
Definitely	The event: a) follows a reasonable temporal association with the study, b) abates upon discontinuation of study procedures, c) cannot be reasonably explained by the patient's clinical condition or other therapy, and d) reappears on re-exposure to the study intervention/procedures.
Unknown	Not enough information exists for the assessment of causality at the time of occurrence.

Signs and symptoms will be graded by the PIs as mild, moderate, severe, or life threatening according to the definitions below (Table 8).

*Table 8 Defining symptom severity for adverse events*

Grade	Definition
Mild	Causing no limitation of usual activity
Moderate	Causing some limitations of usual activities
Severe	Causing inability to carry out usual activities
Life-Threatening	Patient was at immediate risk of death from the event

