Missing data. With high-dimensional phenotyping and the longitudinal character of the study missing data will be inevitable. Handling of missing data will include descriptive analysis of missing data patterns followed by the analysis of reasons for missingness as a nominal response using multinomial logistic regression. Sensitivity analyses will include missing data imputation by predictive-matching algorithms and missing data exclusion under a missing-at-random assumption. We do not expect more than 15% of missing data. If this assumption is not confirmed, multiple imputation approaches will be utilized.

Safety monitoring. Even though no serious side effects are expected from the treatments, in addition to the safeguards in the SMART trial of the Research Project, the Core will monitor safety periodically with 3 interim analyses and one final analysis, using the Fleming design (Fleming, T.R. (1982) One-Sample Multiple Testing Procedure for Phase II Clinical Trials, *Biometrics* 38, 143-151). The analysis will occur after each consecutive recruitment group of another 100 patients has completed their treatments (400 planned patients total under active treatments after drop-out).

Although it is highly unlikely that there will be extensive adverse events related to the study treatment that is any grade 2 or higher because these are all commonly used treatments for cLBP, we have established

an alarm procedure. The alarm procedure is designed to give early warning if the rate of any related AEs, grade 2 or reaches 15% or above. We will consider an alarm when more than 22, 32, 42, and 52 patients show adverse events and classify as related events and are a grade 2 or higher at the 3 interim tests and the final analysis, respectively. Events that may require the study to be discontinued or participant to be withdrawn from the study are described in Section 22.

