## 10 Safety Analyses

Even though no serious side effects are expected from the treatments, in addition to the safeguards in the SMART trial of the Research Project, the Core will monitor safety periodically with 3 interim analyses and one final analysis, using the Fleming design. The analysis will occur after each consecutive recruitment group of another 102 patients has completed their treatments (408 planned patients total under active treatments after drop-out).

Although it is highly unlikely that there will be extensive adverse events related to the study treatment that is any grade 2 or higher because these are all commonly used treatments for cLBP, we have established an alarm procedure. The alarm procedure is designed to give early warning if the rate of any related AEs, grade 2 or reaches 15% or above. The standard rate is assumed to be 10%. We will consider an alarm when more than 21, 31, 41, and 51 patients show adverse events and classify as related events and are a grade 2 or higher at the 3 interim tests and the final analysis, respectively. If the rate of adverse events is indeed at 15% or higher, the suggestion to stop the trial will be generated by this procedure at 253 treated patients or less on average. Errors of both types are set at 5%. A decision that the rate is safe will be suggested after 265 patients on average.

Events that may require the study to be discontinued or participant to be withdrawn from the study are described in the Protocol Section 18.1.6 and Section 22.

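### The relatedness rule lists the two not-related classes as study-related, so read literally the safety alarm counts patients with almost any grade 2 or higher adverse event

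*SAP*

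**What the plan says.** SAP 10.1 and Protocol 23.1.1 carry the same sentence: "Events will be considered study-related if classified by the PIs as definitely not, probably not, possibly, probably, or definitely related". Table 7, which follows it in both documents, has six classes. It defines Definitely Not as "The event is definitely not associated with study" and describes Probably Not as an unlikely association. The sixth class, Unknown ("Not enough information exists for the assessment of causality at the time of occurrence"), is missing from the sentence.

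The classification feeds two rules.

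- **Safety alarm.** SAP 10 states "We will consider an alarm when more than 21, 31, 41, and 51 patients show adverse events", restricted to those that "classify as related events and are a grade 2 or higher at the 3 interim tests and the final analysis". On timing it says "The analysis will occur after each consecutive recruitment group of another 102 patients has completed their treatments", up to 408 patients. It assumes a standard rate of 10%, aims to warn at 15%, and sets both error rates at 5%. Protocol 18.1.5 has the same filter with groups of 100: "We will consider an alarm when more than 22, 32, 42, and 52 patients show adverse events".
- **SAE reporting.** Table 10 in both documents gives related SAEs one row and unrelated or anticipated SAEs another, with different times for reporting to the IRB.

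**The concern.** The sentence makes every event placed in one of the five graded classes study-related. Adverse events are collected whether or not a causal link exists, so relatedness is the only causal filter ahead of the alarm. Under the literal rule that filter removes only the Unknown class.

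The alarm is the only numerical safety boundary in the two documents, and according to the SAP it generates a suggestion to stop the trial. Its 10% and 15% rates are rates of related events. If unrelated events enter the count, the same thresholds are applied to a higher rate and the 5% false-alarm level no longer holds. The related/unrelated split of SAEs in Table 10 also loses its meaning.

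No other sentence in either document sets a cut-off for adverse events. The reasonable-possibility criterion in SAP 10.1.2 and Protocol 23.1.3 belongs to the definition of an unanticipated problem.

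**Working it through.** **What is counted.** The alarm requires an event to be related and grade 2 or higher, and it counts patients.

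| Event | Meaning in Table 7 | Related under the sentence? | Can enter the alarm? |
|---|---|---|---|
| Definitely Not or Probably Not, grade 2+ | not, or not likely, associated | yes | yes |
| Possibly, Probably or Definitely, grade 2+ | some degree of association | yes | yes |
| Unknown, grade 2+ | cannot be assessed | not listed | no |
| Any class, grade 1 | – | – | no |

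**Inputs (SAP 10).** Looks at 102, 204, 306 and 408 patients; alarm when the cumulative count exceeds 21, 31, 41 or 51; standard rate 10%; alarm rate 15%.

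**Method.** Let q be the probability that a patient is counted and S_g the cumulative count at look g, the sum of g independent Binomial(102, q) variables. The alarm probability is the sum over g = 1 to 4 of P(S_g > c_g, with no earlier crossing), where c = (21, 31, 41, 51). It is computed exactly by convolving the binomial distributions look by look. No lower (safe) boundary is used, because the documents print none.

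**Reproducing the plan's figure.** At q = 0.10 the alarm probability is 4.98%, in line with the stated 5% type I error. With lower boundaries of the Fleming type, of about 4, 19 and 35, it is 4.7%. At q = 0.15 it is 91.9%, so the stated 5% type II error is not reproduced. That is a separate matter from the relatedness sentence.

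**Effect of counting unrelated events.** Let r be the share of patients with a related grade 2+ event and u the share with an unrelated one, assumed independent. Then q = 1 − (1 − r)(1 − u). The documents give no value for u, so a range is shown.

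| r | u | q | Alarm probability |
|---|---|---|---|
| 0.10 | 0 | 0.100 | 5.0% |
| 0.10 | 0.02 | 1 − 0.90 × 0.98 = 0.118 | 32% |
| 0.10 | 0.05 | 1 − 0.90 × 0.95 = 0.145 | 87% |
| 0.10 | 0.10 | 1 − 0.90 × 0.90 = 0.190 | above 99.9% |
| 0.05 | 0.05 | 1 − 0.95 × 0.95 = 0.0975 | 3% |
| 0.05 | 0.10 | 1 − 0.95 × 0.90 = 0.145 | 87% |

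Adding the lower boundaries changes the 32% and 87% entries to 30% and 85%. With the Protocol's thresholds (more than 22, 32, 42 and 52, groups of 100), counted rates of 10% and 15% give 2.6% and 86%, so the pattern is the same.

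**The case against.** The strongest reply is that this is a drafting slip for a sentence saying that relatedness will be classified into the following categories. Table 7 and the separate row for unrelated SAEs in Table 10 both show that a distinction is intended, and an investigator who records Definitely Not is unlikely to enter that patient as related. The Data Safety Monitoring Plan is a separate document (Protocol 23) and may contain the cut-off. This is probably right about intent. It does not supply the missing rule: neither document says whether Possibly counts, or how Unknown is treated, and both choices change the count.

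A reader might infer that the alarm counts every adverse event. The documents do not support that. It counts patients, grade 1 events never enter, and Unknown is not on the list.

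A reader might also infer that a false alarm is close to certain. That needs a sizeable rate of unrelated events, for which there is no source, and adverse events are collected by spontaneous report. The 91.9% at a counted rate of 15% is the rule's power at its own design alternative; it represents false alarms only so far as the excess over the related rate is unrelated. At 5% related and 5% unrelated, the alarm probability is about 3%.

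The practical harm is also limited. The alarm produces a suggestion, and the DSMB reviews aggregated adverse events separately. Table 10 requires notice to NIAMS within 48 hours for SAEs of either kind. Only the IRB time differs (7 days or the annual report), and the literal reading errs towards faster reporting.

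**Conclusion.** The point holds in this form: the sentence is wrong as written in both documents, it contradicts Table 7, and no cut-off for related adverse events appears elsewhere in either document. Read literally, it turns an alarm calibrated for related grade 2+ events into one on nearly all grade 2+ events.

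The effect on the alarm ranges from negligible to near-certain firing, depending on rates that the documents do not give. With related events at the 10% standard rate, an unrelated share of only 2% raises the alarm probability from 5.0% to about 32%. With related events at 5%, an unrelated share of 5% leaves it at about 3%. These figures assume independence of related and unrelated events, the SAP thresholds as printed, and no lower boundary. The correction should be made before the alarm is applied. It is a defect of definition and does not show that the alarm has misfired or will.

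**What to change.** In SAP 10.1 and Protocol 23.1.1, replace the sentence with one saying that the PIs will classify relatedness into the Table 7 classes and that only named classes count as related. Possibly, Probably and Definitely is one candidate; the sponsor should confirm that the chosen set matches the basis of the 10% standard rate. State how Unknown is counted, both for the alarm and for SAE reporting. Refer to this definition in the alarm rule (SAP 10, Protocol 18.1.5) and in Table 10, and check that the Data Safety Monitoring Plan uses the same one.

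The cost is one sentence and short cross-references in each document. No new data are needed. If any look has already been tabulated under another reading, its count should be redone.

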#### 10.1.1 Serious Adverse Events (SAE)

A serious adverse event (SAE) is defined as any adverse event that results in one or more of the following outcomes:

- Death
- A life-threatening event
- Inpatient hospitalization or prolongation of existing hospitalization relating to study treatment
- A persistent or significant disability/incapacity hospitalization relating to study treatment
- An important medical event based upon appropriate medical judgment

#### 10.1.2 Unanticipated Problem (UaP) Definition

An unanticipated problem may be either an actual harmful or unfavorable occurrence or any development that potentially increased the likelihood of harm occurring in the future. Assessment Criteria:

- **Unanticipated Severity:** The nature, severity, or frequency of the event(s) or information was NOT expected, given descriptions in the study documents or the characteristics of the subject population being studied.
- **Related:** There is a reasonable possibility that the procedures involved in the research caused the problem.
- **Increased Risk:** The event(s) or information suggests that the research places subjects or others at a greater risk of harm than was previously known or recognized (including physical, psychological, economic, or social harm).

### 10.1.3 Protocol Deviation (PD)

An accidental or unintentional change to, or non-compliance with the research protocol that does not increase risk or decrease benefit or; does not have a significant effect on the subject's rights, safety or welfare; and/or on the integrity of the data. Deviations may result from the action of the subject, researcher, or research staff. Departure from the IRB approved research protocol without prior IRB approval for the variation.

### 10.1.4 Expected Adverse Events

The following table describes expected adverse events in for this study (Table 9). Participant safety monitoring and the process of halting the study is further described in the Protocol Section 23.

*Table 9 Management of expected study adverse events*

Expected Adverse Event	Criteria for Management	Intervention Modification, if any
Biospecimen Collection		
Bruising/Hematoma at site of draw	Participant may verbally report this.	Participant can apply ice to the area.
Discomfort with Physical Therapy		
Muscle soreness Back Pain Fatigue Bruising Psychological distress	Participant reports symptoms lasting more than 2 hours.  Participant verbalizes this.	Participants can stop as needed. Modification may be made to the PT program. Modification to be determined by Physical Therapist.
Mindfulness-based Stress Reduction (MBSR)		
Feelings of de-realization, exacerbation of psychiatric symptoms or clinical deterioration.  Muscle soreness or injury	Clinical worsening of depression and other psychiatric symptom.  Participant verbalizes.	Will be evaluated by clinical psychologist on the study team who may refer the participant for appropriate treatment including emergency service if required. All reports of higher symptoms will be discussed to determine if modifications to the program need to be made.
Acupressure		
Mild bruising at acupressure sites	Participant verbalizes bruising.	The participant is free to withdraw from the intervention if the self-acupressure intervention becomes uncomfortable.
Duloxetine		
Nausea, vomiting, dry mouth, constipation, diarrhea, fatigue, and difficulty sleeping.  Thoughts of self-harm or suicidal ideation	Participant verbalizes experiencing.	Study doctors will evaluate the participant. Participants have the option to stay on lower dose or stopping the medications.  Participants may be referred for appropriate treatment including emergency services if required. Participation can also be discontinued if there is active suicidal ideation.
Quantitative Sensory Testing		

Residual Soreness at testing site Headache, nausea	Participants displaying sustained pain over 48 hours post testing. Participant verbalizes residual headache, or nausea.	Participants will be allowed to take NSAIDs. Stimuli duration and timing may be reduced. Follow up visual stimulation may be omitted or reduced at the follow up visit.
Autonomic Nervous System Monitoring (BIOPAC)		
Irritation to the skin Anxiety or general unease	Participant verbalizes Participant verbalizes	Participants will be instructed they can stop participating at any time. Follow up autonomic nervous system monitoring may be omitted.
MRI		
Claustrophobic Discomfort from noise		Participants may stop the session at any time. The follow up visit may omit the MRI session.

#### 10.1.5 Study Events Reporting Requirements

A timeline for reporting AEs, SAEs, UaPs and Protocol deviations to the NIAMS Executive Secretary and the Institutional Review Board of the University of Michigan are described in Table 10.

Table 10 Timeline for Reporting Study Events to NIAMS and the IRB

Event	NIAMS Executive Secretary who will report to the DSMB and NIAMS	UM IRB
Serious Adverse Event ( Related )	Within 48 hours of the investigator becoming aware of the event	Within 7 days of occurrence notification
Serious Adverse Event (Unrelated or Anticipated)	Within 48 hours of the investigator becoming aware of the event	Annual report to IRB prior to scheduled continuing review
Non-serious adverse events grade 2 or higher ( moderate or greater )	All non-serious adverse events (even those graded as “mild”) should be reported in aggregate as part of the routine DSMP report	Annual report to IRB prior to scheduled continuing review
Any unanticipated problems that are related to the study and indicate risks to subjects	Within 48 hours of the investigator becoming aware of the event	Serious problems within 7 days of occurrence Non-serious problems within 14 days
Privacy violation or breach of confidentiality	If impacting participant safety, report within 48 hours of being notified of the occurrence; all other violations or breaches of confidentiality that do not impact participant safety can be reported as part of the routine DSMP report.	Report to IRB within 7 days Within 24 hours to the UMHS Privacy Office
Protocol deviations	If impacting participant safety, report within 48 hours of being	Annual report to IRB prior to scheduled continuing review

	notified of the occurrence; all other deviations that do not impact participant safety can be reported as part of the routine DSMP report	
--	---	--

#### 10.1.6 Informing Participants of AEs and SAEs

Participants will be informed of any adverse events or serious adverse events if risk-benefit profile is impacted. Events significantly impacting the study integrity that will require a change in protocol and additionally require re-consenting of participants. All active study participants would then be notified. Furthermore, any participant incidental findings will be shared with the PI and conveyed with participant's health care provider.

### 11 Other Analyses

Exploratory, we will analyze the 12 embedded dynamic treatment regimens within the SMART design using the joint model described in section 10.1.1. Additionally, we will consider further tailoring of the embedded dynamic treatment regimens using augmented outcome-weighted learning.

## 13 Appendix A

BACPAC\_SAP\_AppendixA\_Consort\_8-19
